1. PREVIOUS STUDY HISTORY

Has this study ever been reviewed and rejected/disapproved by another IRB prior to submission to this IRB?

No Yes – if yes, please explain:

2. BRIEF SUMMARY OF RESEARCH

- *The summary should be written in language intelligible to a moderately educated, non-scientific layperson.*
- *It should contain a clear statement of the rationale and hypothesis of your study, a concise description of the methodology, with an emphasis on what will happen to the subjects, and a discussion of the results.*
- *This section should be ½ page*

United States citizens receive only half of recommended medical care¹ and a third of the care received is unnecessary². The disparity between usual and evidence based clinical practice is responsible for a third of hospital deaths³ and waste estimated at 380 billion dollars each year⁴. Computerized clinical decision support (CDS) attempts to close the gap by bringing meaningful and relevant evidence to health care providers at the point of decision making. Providers, policymakers, experts and consumers have identified these as key tools to revolutionize health care.⁵⁻⁷ However, the moderate improvements in care seen with CDS⁸⁻¹⁴ have been significantly limited by consistently low provider adoption, estimated at 10%^{15,16}. Thus, there is a critical need to identify strategies to increase provider adoption of CDS.

The central hypothesis of this proposal is that the addition of a theory-informed “nudge” to a CDS tool will address identified behavioral barriers to use and significantly improve adoption by providers. Nudges are applications of behavioral science, defined as positive reinforcement and indirect suggestions that have a non-forced effect on decision making¹⁷. For example, default options for organ donation consent lead to striking differences in enrollment.¹⁸ Previous studies on the impact of nudges on provider behavior have demonstrated exceptional results (i.e. decreased inappropriate antibiotic prescribing from 20% to 4%¹⁹) but have not examined their impact on provider adoption of CDS. We propose to use a behavioral theory-informed process to develop a new CDS tool that includes a nudge that addresses barriers to adoption.

We designed a CDS tool (**PE CALC**) to reduce unnecessary computed tomography pulmonary angiography (CTPA) testing for pulmonary embolus (PE) that is efficacious (37% reduction among tool adopters) when used. However, its overall impact is limited by low provider adoption (15%). Users identified low *social opportunity* [“my colleagues don’t use the tool”], *reflective motivation* [“good

doctors don't need the tool"], *automatic motivation* ["the tool annoys me"] and *psychological capability* ["too many alerts to address"] as primary barriers to adoption on a survey based on the Capability Opportunity Motivation Behavior (**COM-B**) model [*specifies that changing behavior requires changing capability, opportunity and/or motivation*]²⁰. We have identified nudges to address each of these barriers. The overall objective of this training application is to develop and evaluate the feasibility and preliminary efficacy on provider adoption of adding a behavioral theory-informed nudge to PE CALC. By conducting interviews with ED providers, we will develop a prototype of a new tool, "PERK", which will include nudges to PE CALC. We will then perform "Think Aloud" and "Near Live" usability testing. Based on the results of these tests, we will develop PERK and test it in a six month pilot trial in the Emergency Departments (ED) at North Shore University Hospital (NSUH) and Long Island Jewish Medical Center (LIJMC). Our studies will provide us with information about the feasibility, acceptability, and preliminary efficacy of "PERK", as well as broader knowledge of the impact of including nudges in CDS tools to increase provider adoption and decrease unnecessary patient testing.

3. INTRODUCTION/BACKGROUND MATERIAL/PRELIMINARY STUDIES AND SIGNIFICANCE

- *Describe and provide the results of previous work by yourself or others, including animal studies, laboratory studies, pilot studies, pre-clinical and/or clinical studies involving the compound or device to be studied.*
- *Include information as to why you are conducting the study and how the study differs from what has been previously researched, including what the knowledge gaps are.*
- *Describe the importance of the knowledge expected to result*

Clinical decision support (CDS) has been shown to improve quality of care. Meta-analyses of the effect of CDS have shown that providers who use decision support are more likely to order appropriate treatments and provide preventive care services.^{8,21-23} Extensive study of these tools has shown a morbidity decrease of 10 to 18%, placing CDS at the top of the spectrum of quality improvement interventions.²⁴ The expectation of CDS to improve the practice of medicine was communicated with the unprecedented federal resources (\$30 billion) committed to supporting the use of EHRs through the HITECH Act of 2009, where "meaningful use" requirements demand the use of CDS.²⁵ These tools have great potential to improve quality of care.

In spite of the clear benefits of using CDS, meta-analyses have found provider adoption of these tools to be low²⁶ with up to 96% of CDS being overridden²⁷. There is clear evidence of providers not using well thought out CDS, undermining potential clinical impact.²⁸ A systematic review of randomized controlled trials of CDS impact, found four system features to be independently predictive of successful clinical practice improvement.²⁹ Each of these factors improve provider

adoption (automatic triggering, including specific recommendations, workflow integration and computer based support). Improving provider adoption of CDS can help these tools reach their potential to improve quality of care.

One potential method for increasing provider adoption is through the inclusion of nudges. Nudges are defined as positive reinforcement and indirect suggestions that have a non-forced effect on decision making¹⁷. Recent studies have shown that nudges can be effective in influencing provider decision making. For example, a recent large randomized controlled trial evaluating behavioral interventions found a social comparison “nudge” decreased provider antibiotic prescribing for upper respiratory infections from 19.9% to 3.7%.¹⁹ These results were durable at 3 months.³¹ Another study used a simple poster with the clinicians signature committing to antibiotic stewardship to decrease inappropriate antibiotic prescribing by 20% relative to control.³⁰ Even simply changing the grouping of treatment options has demonstrated the ability to significantly impact provider behavior.³²

In our study, we will assess the impact of adding nudges to an existing CDS tool on efficacy provider adoption. We previously developed a tool, PE CALC, to reduce unnecessary imaging in the diagnosis of pulmonary embolism (PE) in the emergency department (ED). One common test for PE, computerized tomography pulmonary angiography (CTPA), is sensitive and specific for PE; however, it is associated with a median of 10 mSV of radiation, the equivalent of 137 chest x rays.³³ A recent study including 2.5 million Medicare emergency visits found utilization to have increased fivefold between 2000 and 2009 with diagnostic yield declining.³⁴ It is now thought that 1.5% to 2% of all future cancers in the United States may be the result of medical radiation.³⁵ Surveyed emergency providers said that about a fifth of all imaging studies ordered are medically unnecessary,³⁶ with factors including fear of missing a low-probability diagnosis and fear of litigation. Clinical prediction rules address these concerns. Clinical prediction rules are validated tools that quantify the contributions the history, physical and laboratory results make towards a diagnosis, prognosis or treatment response.³⁷ They classify patients into low, intermediate and high probability of PE based on key elements of the history and physical exam, establishing pre-test probability before imaging.

Each CTPA carries a 14% risk of contrast induced nephropathy³⁸ and a lifetime malignancy risk that can be as high as 2.76%³⁹. Incidental findings requiring diagnostic follow up are found in 24% of tests, increasing both costs and harms from repeat imaging.⁴⁰ The use of clinical prediction rules to assess pre-test probability before CTPA reduces testing by 25% without any missed PEs.^{41,42} Their routine use by providers would result in 600,000 fewer scans, 84,000 fewer cases of contrast induced nephropathy and prevent 3,000 malignancies as well as 2,000 cancer deaths in the United States every year³⁹.

We based PE CALC on provider preferences, using a well-validated clinical prediction rule perceived as “most useful” by providers surveyed at Northwell Health (the Well’s Score for PE). We implemented this tool in the EDs of NSUH and LIJMC and found that the tool was efficacious when used, with an increase in CTPA yield from 8% to 12% (a 37% reduction in unnecessary CTPAs) among adopters. However, it did not increase CTPA yield for the ED as a whole, as it was only used by 15% of providers. The goal of this study is to add nudges to PE CALC to develop a new tool, which we will call Pulmonary Embolism Risk Kalculator, or PERK. To our knowledge, our study will be the first to use behavioral theory to illuminate the impact of nudges on provider adoption of CDS. We hope that the results of our study will include not only a new CDS tool with higher adoption rate and efficacy than our previous PE CALC, but also new insight into the effects of nudges on provider adoption of CDS tools.

4. OBJECTIVE(S)/SPECIFIC AIMS AND HYPOTHESES

- *A concise statement of the goal(s) of the current study.*
- *The rationale for and specific objectives of the study.*
- *The goals and the hypothesis to be tested should be stated.*

The central hypothesis of this proposal is that the addition of a theory-informed “nudge” to a CDS tool will address identified behavioral barriers to use and significantly improve adoption by providers. Nudges are applications of behavioral science, defined as positive reinforcement and indirect suggestions that have a non-forced effect on decision making. For example, default options for organ donation consent lead to striking differences in enrollment.¹⁸ Previous studies on the impact of nudges on provider behavior have demonstrated exceptional results (i.e. decreased inappropriate antibiotic prescribing from 20% to 4%¹⁹) but have not examined their impact on provider adoption of CDS. We propose to use a behavioral theory-informed process to develop a new CDS tool that includes a nudge that addresses barriers to adoption.

We designed a CDS tool (**PE CALC**) to reduce unnecessary computed tomography pulmonary angiography (CTPA) testing for pulmonary embolus (**PE**) that is efficacious (37% reduction among tool adopters) when used. However, its overall impact is limited by low provider adoption (15%). Users identified low *social opportunity* [“my colleagues don’t use the tool”], *reflective motivation* [“good doctors don’t need the tool”], *automatic motivation* [“the tool annoys me”] and *psychological capability* [“too many alerts to address”] as primary barriers to adoption on a survey based on the Capability Opportunity Motivation Behavior (**COM-B**) model [*specifies that changing behavior requires changing capability, opportunity and/or motivation*]²⁰. We have identified nudges to address each of these barriers. The overall objective of this training application is to develop and

evaluate the feasibility and preliminary efficacy on provider adoption of adding a behavioral theory-informed nudge to PE CALC. We will address this with the following Specific Aims:

AIM 1: To develop nudges designed to address identified behavioral barriers to adoption. We will create four nudges designed to address four identified barriers of tool use, using on our survey results and COM-B as a framework.

AIM 2: To conduct iterative usability testing on an evolving prototype of a new tool, “PERK”. This will involve both qualitative and quantitative assessments of ease of use of “PERK”. We will perform “think aloud” and “near live” testing to develop a prototype that will be revised and evaluated.

AIM 3: To evaluate the feasibility, acceptability and preliminary efficacy on provider adoption of a new tool compared to the current tool, in a pilot trial. We will conduct a 6 month pre-post analysis of “PERK” by comparing it to retrospective data from the first 6 months of PE CALC. Our primary feasibility outcome is post-pilot provider satisfaction. Secondary outcomes include stakeholder acceptability.

***H1:** PERK will demonstrate higher rates of provider satisfaction as compared to PE CALC.* Our primary efficacy outcome is increased provider adoption. Secondary outcomes include increased CTPA yield [% of positive tests], and decreased CTPA ordering. ***H2:** “PERK” will demonstrate higher provider adoption as compared to PE CALC.*

5. RESOURCES AVAILABLE TO CONDUCT THE HUMAN RESEARCH

- *Explain the feasibility of meeting recruitment goals of this project and demonstrate a potential for recruiting the required number of suitable subjects within the agreed recruitment period*
 - *How many potential subjects do you have access to?*
- *Describe your process to ensure that all persons assisting with the trial are adequately informed about the protocol and their trial related duties and functions*

The study will collect data from the Emergency Departments (ED) of both North Shore University Hospital (NSUH) and Long Island Jewish Medical Center (LIJMC). Eligible participants for all three aims will be medical doctors and physician assistants working full time in either of these Emergency Departments (86 eligible at NSUH; 63 eligible at LIJMC). We will recruit from within this pool for AIM 1 and AIM 2. For AIM 3, all eligible providers will be automatically enrolled, as we will be collecting data from the EHR regarding the use of PERK.

All persons assisting with the trial will review the research protocol and be informed of their specific duties prior to the commencement of any research activities. We will also hold a study launch meeting for all involved in the research.

6. RECRUITMENT METHODS

- *Describe the source of potential subjects*
- *Describe the methods that will be used to identify potential subjects*
- *Describe any materials that will be used to recruit subjects. A copy of any advertisements (flyers, radio scripts, etc.) should be submitted along with the protocol.*
- *If monetary compensation is to be offered, this should be indicated in the protocol*

Eligible subjects for all three aims of this study will be medical doctors and physician assistants working full time at NSUH or LIJMC. This includes residents in the Emergency Medicine/Internal Medicine program.

For AIM 1, potential subjects will be identified using the Electronic Medical Records (EMR) based on PE CALC use. We will contact participants via our secure email system. We will inform participants about the study, offering a \$50 reimbursement for their time.

In addition, we will contact department heads at NSUH and LIJMC, as well as administrators, attendings, chief residents, administrative residents, and head PAs, and request names of potential participants for Aims 1 and 2. We will email the identified providers, mentioning the person who recommended that they might be interested in participating, and asking if they would like to participate in our study. Alternatively, we will ask department heads, administrators, or other faculty or staff to email potential participants and inform them of our study. We may also present our study at ED faculty meetings and/or resident meetings to raise awareness of our study. Alternatively, we will ask department heads, administrators, or other faculty or staff to present our study in information sessions to promote participation.

For AIM 2, eligibility and recruitment methods will be the same as for AIM 1, as indicated in the previous paragraph. We will contact participants using the health system email. We may also ask department heads, administrators, or other faculty or staff to distribute and/or display flyers to promote our study. The flyer may also be distributed through the physician Teams chat. We will inform potential participants and solicit interest, offering a \$50 reimbursement for their time. There may be one follow-up phone call.

For AIM 3, full time ED providers will be eligible. We will conduct a pilot trial of PERK among 150 Emergency Medicine providers at NSUH and LIJMC. We expect 150 providers who meet the inclusion criteria to be in each of the pre- and post-groups.

7. ELIGIBILITY CRITERIA

- *Describe the characteristics of the subject population, including their anticipated number, age, ranges, sex, ethnic background, and health status. Identify the criteria for inclusion or exclusion of any subpopulation.*

- *Explain the rationale for the involvement of special classes of subjects, such as fetuses, pregnant women, children, prisoners or other institutionalized individuals, or others who are likely to be vulnerable. You cannot include these populations in your research, unless you indicate such in the protocol*
- *Similarly, detail exclusionary criteria: age limits, special populations (minors, pregnant women, decisionally impaired), use of concomitant medications, subjects with other diseases, severity of illness, etc.*

Eligible subjects for all three aims of this study will be medical doctors and physician assistants working full time at NSUH or LIJMC. Participants will not be excluded by gender, race, or ethnicity. The providers in this study are expected to reflect the gender and racial/ethnic composition of the Emergency Department providers at North Shore University Hospital (NSUH) and Long Island Jewish Medical Center (LIJMC), who are approximately 35% women, 55% non-Hispanic White, 32% Asian, 6% Hispanic/Latino (of any race), 3% Black, and 4% multiracial/other. As this study focuses on adult medical providers, children will not be included. We anticipate adult participants age 25-70.

For AIM 1, we expect to recruit 12 participants to complete semi-structured interviews; however, we will recruit until thematic saturation is achieved.

For AIM 2, we expect to recruit 10 participants (5 for “Think Aloud” testing; 5 for “Near Live” testing); however, we will recruit until thematic saturation is achieved.

For AIM 3, we expect to include 150 providers who meet the inclusion criteria in the prospective cohort pilot study, and 150 in the retrospective cohort control group.

8. NUMBER OF SUBJECTS

- *Indicate the total number of subjects to be accrued locally. If applicable, distinguish between the number of subjects who are expected to be pre-screened, enrolled (consent obtained), randomized and complete the research procedures.*
- *If your study includes different cohorts, include the total number of subjects in each cohort.*
- *If this is multisite study, include total number of subjects across all sites*

For AIM 1, we expect to recruit 12 participants to complete semi-structured interviews; however, we will recruit until thematic saturation is achieved.

For AIM 2, we expect to recruit 10 participants (5 for “think aloud” testing; 5 for “near live” testing); however, we will recruit until thematic saturation is achieved.

For AIM 3, we expect to include 150 providers who meet the inclusion criteria in the prospective cohort pilot study, and 150 in the retrospective cohort control group.

9. STUDY TIMELINES

- *Describe the duration of an individuals participation in the study*
- *Describe the duration anticipated to enroll all study subjects*
- *The estimated date of study completion*

Enrollment will occur on a rolling basis throughout the testing period for AIM 1. Interviews for AIM 1 will take place during the first six months of Year 1, beginning in January 2019. Each participant will be interviewed for a 20-30 minute period, during which they will also be consented. It is possible that participants will be contacted again during the six month interview period for clarification; however, we do not anticipate contacting most providers outside of their interview sessions. Following the interview period, we will develop a “PERK” prototype in the second half of Year 1.

Enrollment will occur on a rolling basis throughout the testing period for AIM 2. For AIM 2, usability testing and iterative revision of the prototype will take place during Year 2 of the grant. Each participant will take part in a usability testing session approximately 20-30 minutes in duration, during which they will also be consented. Participants will also be given the option to fill out the pre-session questionnaire, consent form, and Audio Visual Authorization form on REDCap prior to their session. It is possible that participants will be contacted again during the one year period of usability testing sessions for clarification; however, we do not anticipate contacting most providers outside of their usability sessions.

During the first half of Year 3, we will develop the new PERK tool. In the second half of Year 3, we will recruit for the pilot clinical trial in AIM 3. The new PERK tool will be active for 6 months, and all full-time employed providers working in the emergency department at NSUH and LIJMC will be eligible for participation. We will perform the pilot trial in Year 4. The clinical decision support tool will be integrated into the electronic medical record and will be accessible for all full-time employed emergency department providers (n=150). Providers will be trained on using the tool through 30 minute sessions delivered during emergency department grand rounds. Additional education sessions will be delivered to continue participant engagement over time. In the second half of Year 4, to assess feasibility, providers will be contacted by email to participate in a post-pilot satisfaction survey. Reminder emails to complete the survey will be sent out up to five times. To assess acceptability, providers will be contacted by email to participate in one-time stakeholder interviews. A follow up phone call will be conducted with providers to provide participant information and solicit interest. The pilot trial will end in June 2022. We will complete our analyses in the first quarter of Year 5. The anticipated end date for this grant is August 31st, 2023.

10. ENDPOINTS

- *Describe the primary and secondary study endpoints*
- *Describe any primary or secondary safety endpoints*

The endpoint of this study is provider adoption of the PERK tool. Secondary outcomes include increased CTPA yield [% of positive tests], and decreased CTPA ordering.

Our primary feasibility outcome is post-pilot provider satisfaction.

11. RESEARCH PROCEDURES

- *Include a detailed description of all procedures to be performed on the research subject and the schedule for each procedure.*
- *Include any screening procedures for eligibility and/or baseline diagnostic tests*
- *Include procedures being performed to monitor subjects for safety or minimize risks*
- *Include information about drug washout periods*
- *If drugs or biologics are being administered provide information on dosing and route of administration*
- *Clearly indicate which procedures are only being conducted for research purposes.*
- *If any specimens will be used for this research, explain whether they are being collected specifically for research purposes.*
- *Describe any source records that will be used to collect data about subjects*
- *Indicate the data to be collected, including long term follow-up*

In AIM1, we will conduct semi-structured interviews with low, intermediate, and high users of the current tool, PE CALC (n=12 total, 4 each, continuing until data saturation) to refine our understanding of barriers to tool use and receive feedback on nudges' acceptability and ability to address identified barriers. Guided by our preliminary survey data and the COM-B framework, we will develop an interview guide. The interview will have three goals: 1) refinement of the four most prevalent barriers, 2) assessment of how well each nudge addresses the behavioral barrier, and 3) acceptability of the nudge. [name] will conduct structured interviews at NSUH, LIJMC, [name], and other clinical sites including [name] with [name], PhD, an experienced researcher. The interviews will be audio recorded (using two digital voice recorders; one for backup in case of technical failure) and professionally transcribed. The guide will be revised based on the ongoing analysis of interview data.

In AIM 2, we will perform iterative usability testing of an evolving prototype of "PERK". We will build the prototype into the wireframing tool, Axure. The PERK prototype will add 4 small nudges to PE CALC. Usability of the prototype will be tested in two steps, "Think Aloud" and "Near Live" (n=5 participants each). During "Think Aloud" testing, participants verbalize their thought processes while interacting with the prototype. Participants will be given written clinical scenarios with low, intermediate, or high probability PE cases and asked to complete the specific steps necessary to use the tool. During

“Near Live” testing, participants will interact with a standardized patient pretending to have a low, intermediate, or high probability of PE. Participants will use the tool as they would during a real patient encounter to highlight higher level workflow usability issues.

All five participants for each round of testing will interact with the prototype at each step. The tool will be modified after “Think Aloud” and again after “Near Live” based on testing results. Before every session participants will be asked to complete a questionnaire to gather demographic information. They will be given a laptop with the PERK prototype and screen capture software. After every session they will complete a questionnaire to collect retrospective impressions of the tool, and a quantitative survey, the System Usability Scale. Each session will be audio-taped and Morae usability testing software will be used to screen-capture record all human-EHR interactions.

AIM 2 participants will be tested either in person or remotely via videoconferencing (such as with Microsoft Teams). Participants being tested remotely will fill out consent forms, the Audio Visual Authorization Form, and the surveys on REDCap. Participants being tested in person will be given the option to fill out these forms on REDCap or on paper. Audio and screen capture recordings (using Hypercam, Teams, or Morae) will be taken for each session. Prior to or at the beginning of each session, participants will fill out the Usability Pre-session Questionnaire. At the end of each session, participants will verbally answer questions from the Post-session Interview and PERK Tool (Feedback Survey Aim 2) documents; they will also fill out the System Usability Scale (on REDCap for remote testing, on paper or REDCap for in-person testing).

In AIM 3, we will conduct a pilot trial to evaluate the feasibility, acceptability, and preliminary efficacy on provider adoption of the new tool, “PERK”, compared to the current PE CALC tool. This will consist of a six month prospective cohort pilot study with a retrospective cohort control group. All full time ED providers at NSUH and LIJMC will be eligible for participation. Training on PERK use will be conducted as a presentation during ED Grand Rounds. This will be led by [name] and a research coordinator. It will last about 30 minutes with three basic components: 1) overview of the evidence supporting tool use, 2) hands-on session to practice using the tool, and 3) question and answer session. Similar educational training was conducted before launching the current tool, PE CALC.

For the pilot study, we will use EHR reporting data to generate a PERK monitoring dashboard. The dashboard will include trigger rates (percentage of ED patients for which the tool triggers), adoption rates (the percentage of times the provider completes the calculator once the tool is triggered), CTPA order rates (percentage of total ED patients for which a CTPA is ordered for the evaluation of PE), and CTPA yield (the percentage of tests ordered to evaluate for PE that are positive for PE).

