For AIM 3, we will determine the feasibility of PERK using post-pilot provider satisfaction surveys, where mean scores for each response on a Likert scale will be reported with standard deviations and 95% confidence intervals. Acceptability will be determined from post-pilot stakeholder interviews with providers, nurses and the ED chairs at both institutions. Preliminary efficacy will be assessed by comparing provider adoption of PERK to provider adoption for the first six months of PE CALC. Providers in the pre- and post- groups will be summarized using descriptive statistics. Provider age, gender, race and type (attending vs. resident vs. physician assistant) will be compared between the two groups using two-sample t-test or Wilcoxon Rank Sum test for continuous variables and Chi-squared or Fisher's exact test for categorical variables. Since the variability of the adoption rate of PERK for each provider depends, in part, on the number of encounters, providers with larger numbers of encounters should carry more weight. Therefore, a weighted two-sample t-test will be used to test the difference in the weighted means of adoption rates between the groups. Weighted least squares linear regression with number of encounters as weight for each observation (provider) will be performed, to see whether there is difference in the adoption rate between the two groups after controlling for provider age, gender, race, type and other confounding variables.

Power Calculations: We expect 150 providers who meet the inclusion criteria to be in each of pre- and post- groups. We also assume the mean adoption rate of the pre group to be 15% with the standard deviation of 10% based on the historical data, and the mean adoption rate of the post- group to be 20%, 25% and 30% with equal standard deviation. With the sample size of 150 in each group, there will be at least 99% power to detect the difference of 5%, 10% and 15% in the mean adoption rates using a two-sided two-sample t-test at a significance level of 0.05. We are aware that the weighted two-sample t-test should be used to calculate the power. However, due to the lack of information about weights, the unweighted two-sample t-test was used instead.

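### Adoption is measured per trigger, so a change in how often the tool fires could raise the primary outcome without more use; the plan does not check for this

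*Combined protocol and SAP*

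**What the plan says.** Section 4, Aim 3, states: "Our primary efficacy outcome is increased provider adoption". H2 is that adoption will be higher with PERK than with PE CALC, and Section 10 names adoption as the study endpoint. The only operational definition is in Section 11, in the list of measures for the PERK dashboard: "adoption rates (the percentage of times the provider completes the calculator once the tool is triggered". The same list includes "trigger rates (percentage of ED patients for which the tool triggers".

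Section 12 sets the comparison: "Preliminary efficacy will be assessed by comparing provider adoption of PERK to provider adoption for the first six months of PE CALC". It plans a weighted two-sample t-test and a weighted regression adjusted for provider characteristics and unspecified other confounders. Trigger rate is not an endpoint in Section 10, is not a named covariate, and is not compared between periods.

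On the intervention, Section 4 lists "too many alerts to address" among four primary barriers and adds: "We have identified nudges to address each of these barriers". Aim 1 says: "We will create four nudges designed to address four identified barriers of tool use". Section 11 says: "The PERK prototype will add 4 small nudges to PE CALC", and has the tool modified after each of the two rounds of usability testing. No section says what event fires the tool, whether it can fire more than once for a patient, or whether the firing criteria in the pilot will be those of the PE CALC period.

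**The concern.** A ratio of completions to triggers can rise because providers complete the calculator more often, or because triggers that would have been dismissed no longer occur. The first is the behaviour change that the central hypothesis describes. The second can happen with no additional use of the tool.

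Two features of this trial make the distinction matter. One target barrier is alert burden and the design is still open to revision, so a change in firing cannot be ruled out. The control is also retrospective, so no concurrent group would show such a change. At 15% adoption, 85 of every 100 triggers are not completed, so the denominator consists mostly of events whose loss would raise the ratio. As written, Section 12 cannot tell the two explanations apart.

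**Working it through.** **Inputs (Section 12).** Pre-group mean adoption 15%, SD 10 points, 150 providers per group, two-sided alpha 0.05, post-group means of 20%, 25% and 30% with equal SD, stated power at least 99%.

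**Step 1: the plan's own figure.** SE = 10 × √(2/150) = 1.155. For a 5-point difference, 5/1.155 = 4.330; 4.330 − 1.960 = 2.370; Φ(2.370) = 99.1%. The noncentral t also gives 99.1%. The stated power reproduces and is not in question.

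**Step 2: effect of a change in firing.** Let *a* be baseline adoption, *x* the fraction of triggers lost, and *q* the completion rate those triggers would have had. With provider behaviour on the remaining triggers unchanged,

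new adoption = (a − xq) / (1 − x).

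The documents give no trigger rate, so *x* and *q* are assumptions, shown as a range. With a = 15% and x = 25%:

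| q | New adoption | Completions per 100 original triggers | Chance of a significant rise (SD 10 in both groups) |
|---|---|---|---|
| 0% | 15.00/75 = 20.0% | 15.00 | 99.1% |
| 5% | 13.75/75 = 18.3% | 13.75 | Φ(3.333/1.155 − 1.960) = Φ(0.927) = 82% |
| 10% | 12.50/75 = 16.7% | 12.50 | Φ(1.667/1.155 − 1.960) = Φ(−0.517) = 30% |
| 15% | 11.25/75 = 15.0% | 11.25 | 2.5% (no effect) |

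In the two middle rows adoption rises while completed calculators fall. If q exceeds 15%, adoption falls.

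**Step 3: the SD.** In the q = 0% row, each provider's rate is divided by 0.75, which would scale the post-group SD to 10/0.75 = 13.33. Then SE = √((100 + 177.8)/150) = 1.361; 5/1.361 = 3.674; Φ(3.674 − 1.960) = 95.7%. The range for this row is therefore about 96% to 99%.

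**Step 4: other cuts, all lost triggers dismissed (q = 0%).** New adoption = 15/(1 − x).

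| x | New adoption | Chance of significance, equal SD / scaled SD |
|---|---|---|
| 10% | 16.7% | 30% / 28% |
| 20% | 18.75% | 90% / 82% |
| 25% | 20.0% | 99.1% / 95.7% |
| 40% | 25.0% | about 100% / about 100% |
| 50% | 30.0% | about 100% / about 100% |

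A 25% cut of this kind removes 25/85 = 29% of the dismissed triggers. Cuts of 25%, 40% and 50% match the three effects in the power section, but the documents support none of them as a forecast.

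These figures use the unweighted test, as the plan's power section does. Section 12 weights providers by number of encounters without saying whether an encounter is a trigger. If it is, a change in firing also changes the weights.

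**The case against.** The strongest reply is that nothing in the documents says PERK will fire less often. Nudges are defined there as positive reinforcement and indirect suggestion, not alert suppression. The alert complaint is filed under psychological capability and may refer to total alert load, not to this tool. A nudge could ease it with firing unchanged. This stands: a reader might infer from the barrier list that fewer triggers is a planned feature, and the text does not support that.

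Nor does a fall in triggers raise adoption by itself. A fall unrelated to completion leaves it at 15%, as the last row of Step 2 shows. A reader might also infer that fewer CTPA orders would mean fewer triggers, but no section says that a CTPA order fires the tool.

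Response to the tool when it is offered is also a legitimate thing to measure, and it is what H2 literally concerns. Completions per ED patient is a different quantity that also reflects case mix. Requiring both to rise could reject a real gain. Assume one firing per patient, triggers falling from 10 to 7 per 100 patients, and adoption truly rising from 15% to 20%: completions go from 10 × 0.15 = 1.5 to 7 × 0.20 = 1.4. This stands, and it argues against a two-part success rule.

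Finally, the dashboard already tracks trigger rate, so a shift within the pilot would be visible. This helps only in part: the dashboard is described for PERK, and no comparison with the PE CALC period is planned.

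**Conclusion.** The concern holds as a conditional one. The primary efficacy outcome has a denominator produced by the tool under test, and the plan neither states that firing criteria are constant across periods nor compares trigger rates. If firing falls and the lost triggers were less likely than average to be completed, adoption rises without more use.

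Under an assumed 25% cut, the shift ranges from 0 to 5 points as the completion rate of the lost triggers goes from 15% down to 0%. At the 5-point end, the test on the plan's power inputs would be significant about 96% (scaled SD) to 99% (equal SD) of the time. The size of any cut, and which triggers would be lost, are assumptions.

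The documents do not support the stronger conclusions that PERK is designed to fire less, that the adoption definition is invalid, or that the power calculation is wrong.

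**What to change.** In Section 12:

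1. Report completed calculators per 100 ED patients in both periods, with a 95% CI for the difference, beside the primary adoption result. Count completions directly from the EHR. Do not multiply trigger rate by adoption rate: Section 11 defines the first per patient and the second per firing, so the product is right only if the tool fires once per patient.
2. Report triggers per 100 ED patients in both periods, and state whether the trigger criteria are the same.
3. Interpret H2 in light of both measures. Describe a rise in adoption without a rise in completions per ED patient as a possible denominator effect. Keep adoption as the primary outcome, and do not make a rise in both measures a condition for supporting H2.

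The cost is one extra supporting analysis and some wording. Completions and triggers in both periods are already needed to compute adoption, and ED patient counts in both periods are needed for the CTPA ordering outcome. The downside is a more qualified claim if triggers fall. Because completions per ED patient also depends on case mix, it supports the primary outcome and does not replace it.
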